## **3.3.2       Safety**

During the Post-treatment Phase, treatment emergent changes in physical findings, vital signs, clinical laboratory parameters, and the development of adverse events (AEs) will be the primary assessments of safety. During the Long-term Outcomes Phase, the development of any serious adverse reactions (SARs) will be monitored. Sections 9 and 15.1 provide the guidelines and definitions for AE reporting.

### **3.3.2.1    Medical History, Maternal History, and Demographics**

A complete medical history, including the maternal history parameters shown in Table 3-4, and demographics will be obtained at Screening. Any changes to medical history that occur between the Screening and Baseline assessments should be recorded. Past or present illnesses, current medications, and history of medication allergies should be recorded. Any significant changes to the subject's medical condition must be documented throughout the course of the Post-treatment Phase.

**Table 3-4 Maternal History Parameters**

Maternal age/race/ethnicity	Reason for delivery (preeclampsia, eclampsia, rupture of membrane, etc)
Diagnosis of chorioamnionitis during pregnancy	Mode of delivery
Medications during pregnancy (corticosteroids, medications used to treat pre-eclampsia)/delivery	Receipt of IV magnesium

**3.3.2.2 Physical Examination/Chest X-ray**

A complete physical examination, including a CXR, will be conducted at Baseline (prior to randomization) and at 36 Weeks PMA. The most recent CXR prior to randomization and 36 Weeks PMA can be used without being retaken. All treatment emergent clinically significant findings during the Post-treatment Phase will be recorded as AEs.

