### 3.2 OVERALL SCHEDULE OF TIMES AND EVENTS

**Table 3-1 Schedule of Times and Events – Post-treatment Phase**

Study Procedures	Screening a	Baseline a	Post-treatment Phase					
			24 Hours Postdose	72 Hours Postdose	7 Days Postdose	Weekly Until 35 Weeks PMA	36 Weeks PMA b	40 Weeks PMA/ Hospital Discharge b,c
Study Day	-48 Hours to Baseline	1	2	4	8	15, 22, 29, 36, 43, 50, 57, 64, 71, 78, and 85	50 up to 88	78 up to 116
Visit Window			±4 hours	±4 hours	±1 day	±2 days	±2 days	±2 days
Parental Informed Consent	X							
Subject Eligibility	X	X						
Medical History	X							
Demographics	X							
Maternal History	X							
Weight	X	X				X	X	X
Length and Head Circumference		X					X	X
CXR d		X					X	
Clinical Laboratory Assessments e		X		X			X	
Predefined Complications of Prematurity		X	X	X	X	X	X	X
Vital Signs f		X	X	X	X	X	X	X
Physical Examination		X					X	
Mean Airway Pressure g		X	X	X	X	X	X	X
Oxygen Saturation h		X	X	X	X	X	X	X
Respiratory Severity Score i		X	X	X	X	X	X	X
Tracheal Aspirate j		X		X	X			
Concomitant Medications		X	X	X	X	X	X	X
Adverse Events k	X	X	X	X	X	X	X	X
Randomization		X l						
UNEX-42/Placebo Administration		X l						
Incidence and Severity of BPD m							X	

Study Procedures		Screening a	Baseline a	Post-treatment Phase					
Assessment Period	Study Day			24 Hours Postdose	72 Hours Postdose	7 Days Postdose	Weekly Until 35 Weeks PMA	36 Weeks PMA b	40 Weeks PMA/ Hospital Discharge b,c
Study Day		-48 Hours to Baseline	1	2	4	8	15, 22, 29, 36, 43, 50, 57, 64, 71, 78, and 85	50 up to 88	78 up to 116
Visit Window				±4 hours	±4 hours	±1 day	±2 days	±2 days	±2 days
Duration of Mechanical Ventilation, Supplemental Oxygen Therapy, and Hospitalization									X n

Abbreviations: AE, adverse event; CXR, chest x-ray; FiO2, fraction of inspired oxygen; GA, gestational age; PMA, postmenstrual age; RSS, Respiratory Severity Score

a The Screening and Baseline assessments may be combined; however, all entry criteria must be confirmed prior to randomization.

b The days of the 36 and 40 Weeks PMA assessments are based on each subject's GA determined during Screening based on local standard practice.

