k All AEs will be documented from the time of informed consent until the time screen failure is documented, or until the subject is either discontinued from the study or all 40 Weeks PMA/Hospital Discharge assessments have been completed and should be followed until either resolution (or return to normal or baseline values), until they are judged by the Investigator to no longer be clinically significant, or for at least 30 days if the AE extends beyond the Post-treatment Phase.

l UNEX-42 or placebo will be administered after all other Day 1 assessments are completed, with the exception of vital signs (see footnote f).

m This assessment to be performed at 36 Weeks PMA or at Hospital Discharge, whichever comes first (see Section [3.3.1](#)).

n For each parameter, the total number of days from Baseline to the 40 Weeks PMA/Hospital Discharge will be calculated.

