### **3.3.2.6 Clinical Laboratory Parameters**

Blood samples for the clinical chemistry and hematology analyses will be collected at Baseline (randomization) and repeated at the 72 hours postdose and the 36 Weeks PMA assessments to evaluate for study treatment-emergent changes. For Baseline, the clinical laboratory assessments may utilize the laboratory assessments obtained as standard of care treatment within the last 24 hours in lieu of drawing blood for the sole purpose of the study. Any study-required blood tests should be obtained at the same time a blood sample is being collected for clinical purposes, if possible. Values for the following parameters will be obtained:

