### 7.4 40 WEEKS PMA/HOSPITAL DISCHARGE

At the end of the Post-treatment Phase (40 Weeks PMA/Hospital Discharge), final assessments for each subject will be performed according to [Table 3-1](#). If a subject discontinues from the study prematurely, 40 Weeks PMA/Hospital Discharge assessments should occur if possible.

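### An infant who leaves between 72 hours and 36 weeks PMA has one scheduled post-dose laboratory set and no scheduled post-dose examination, because the discharge/early-discontinuation visit includes neither

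*Protocol*

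**What the plan says.** Protocol 3.3.2 states, for the period from dosing to the exit visit, that "treatment emergent changes in physical findings, vital signs, clinical laboratory parameters, and the development of adverse events (AEs) will be the primary assessments of safety". The formal primary endpoints in Protocol 10.3.1 and SAP 2.2.1 include absolute values and changes from Baseline for laboratory parameters. They do not list physical findings.

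The schedule for these assessments is:

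- Physical examination and chest x-ray: Protocol 3.3.2.2 says that they "will be conducted at Baseline (prior to randomization) and at 36 Weeks PMA". Table 3-1 marks the same two visits.
- Laboratory tests: Protocol 3.3.2.6 has them drawn at Baseline and "repeated at the 72 hours postdose and the 36 Weeks PMA assessments to evaluate for study treatment-emergent changes". Table 3-1 agrees.
- Exit visit: Protocol 7.4 says, "If a subject discontinues from the study prematurely, 40 Weeks PMA/Hospital Discharge assessments should occur if possible". Footnote c to Table 3-1 says the same. In that column the examination, laboratory and chest x-ray rows are blank.
- BPD assessment: footnote m to Table 3-1 reads, "This assessment to be performed at 36 Weeks PMA or at Hospital Discharge, whichever comes first". The examination and laboratory rows carry no such rule. Footnote d lets the most recent chest x-ray before randomization or before 36 weeks PMA be used, but does not mention discharge.

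**The concern.** The protocol foresees that some infants will go home before 36 weeks PMA and makes provision for that in the BPD row alone. Three other procedures due at the same visit are left without a fallback. An infant discharged or withdrawn before then passes through an exit visit that does not ask for them, and once the infant has gone the data cannot be recovered.

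For laboratory tests, what is lost is the final value of a formal primary endpoint. For the examination, it is the only scheduled comparison with Baseline. Leaving early may also be related to outcome: an infant improves and goes home, or parents withdraw after an event. The infants without these data may then differ systematically from those who stay, and SAP 8.1 rules out imputation, so nothing in the analysis would make up for the gap.

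**Working it through.** **Inputs.** Gestational age at birth 23 weeks 0 days to 26 weeks 6 days and postnatal age 3 to 14 days at randomization (Protocol 4.1); study days and visit marks (Table 3-1); 4 active infants per cohort (Protocol 3.5).

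**Step 1: reproduce the stated timing.** Days from dosing to a target PMA = 7 × target weeks − gestational age at birth in days − postnatal age at dosing.

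- 36 weeks, shortest: 252 − 188 − 14 = 50 days. Longest: 252 − 161 − 3 = 88 days.
- 40 weeks, shortest: 280 − 188 − 14 = 78 days. Longest: 280 − 161 − 3 = 116 days.

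Table 3-1 gives 50 to 88 and 78 to 116, so its figures are reproduced. Strictly, these are elapsed days; with dosing on Day 1 they would be Study Days 51 to 89 and 79 to 117. The one-day difference lies inside the ±2-day window and does not matter here.

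**Step 2: timing of the only scheduled post-dose examination.** 50/7 = 7.1 weeks and 88/7 = 12.6 weeks after dosing.

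**Step 3: gap between scheduled laboratory draws.** The 72-hour draw is on Study Day 4. From there to the 36-week visit is 50 − 4 = 46 to 88 − 4 = 84 days.

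**Step 4: count scheduled post-dose procedures from the columns of Table 3-1.**

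| Infant | Physical examinations | Laboratory sets |
|---|---|---|
| Followed to 36 weeks PMA or beyond | 1 | 2 (72 h, 36 weeks) |
| Leaves after 72 h, before 36 weeks PMA | 0 | 1 (72 h) |

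The exit column adds nothing to either count. It does contain weight, length, head circumference, complications of prematurity, vital signs, respiratory measures, concomitant medications and adverse events.

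**Step 5: illustration of size.** The documents give no rate of discharge or withdrawal before 36 weeks PMA, so an expected number cannot be computed. One such infant on active treatment would be 1/4 = 25% of a dose group.

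**The case against.** The strongest reply is that safety surveillance does not hang on the examination form. Protocol 3.3.2.2 sends every treatment-emergent finding of clinical importance into the adverse event record. Protocol 3.3.2.1 requires significant changes in the infant's condition to be documented throughout the phase, and Protocol 15.1 has the investigator review all diagnostic and laboratory results as they arrive. Vital signs are taken seven times on Day 1 (Protocol 3.3.2.3). Vital signs, respiratory measures and complications of prematurity are recorded at 24 hours, 72 hours and 7 days, and laboratory tests at 72 hours. These are intubated inpatients. All of this stands. A reader might infer from the schedule that acute physical findings cannot be detected, or that early leavers are never examined after dosing. The documents support neither. They show only that no examination is scheduled and that findings are not systematically compared with Baseline.

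It is also true that physical findings are absent from the primary endpoint list, and that SAP 12.1 has no listing titled for them. That weakens the examination part of the point and shows that Protocol 3.3.2 and the endpoint list need reconciling. It does not touch the laboratory part, since laboratory change is a listed primary endpoint.

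Protocol 8.1 contains a general request that sites try to complete whatever is scheduled before the infant goes home. It names no procedure and does not move the 36-week ones to an earlier date. Footnote d already covers part of the chest x-ray gap, because an existing film can be used. Finally, exit assessments are only asked for where feasible, and no added row would help after a death or a full withdrawal of consent.

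**Conclusion.** The gap is real but limited. An infant who leaves between 72 hours and 36 weeks PMA loses one of two scheduled post-dose laboratory sets and the only scheduled post-dose examination, while the BPD assessment at the same visit has a fallback. This follows from Table 3-1 and its footnotes without further assumption. How many infants would be affected is unknown. The 25% figure is what one active infant represents in a group of 4, and should not be read as an expected loss.

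The absence of an examination at 24 hours, 72 hours and 7 days is a weaker point, given the other data taken at those visits. Recording one there is optional.

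SAP 1.1 reports that the study was terminated with 3 subjects randomized and that only listings will be produced. An edit now cannot change those data. The point matters for a resumed or successor protocol, and for describing what the listings can and cannot show about infants who left early.

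**What to change.** Extend the footnote m rule to the physical examination, clinical laboratory and chest x-ray rows of Table 3-1, and align Protocol 3.3.2.2, 3.3.2.6 and 7.4. Each would be done at 36 weeks PMA or at hospital discharge or early discontinuation (where possible), whichever comes first. Clinically obtained samples and the most recent film should be acceptable, as the protocol already allows for Baseline laboratory tests and for chest x-rays. This brings forward procedures already planned. The cost is slightly more data entry and at most one re-timed blood sample in an early leaver.

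Optional: at the existing 24-hour and 72-hour visits, record the findings of the routine inpatient examination as change from Baseline. The cost is two short eCRF pages.

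Also reconcile Protocol 3.3.2, which names physical findings, with Protocol 10.3.1, SAP 2.2.1 and SAP 12.1, which do not. For the present study, the report should state which infants, if any, left before 36 weeks PMA and so lack the later laboratory values and the examination.

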**3.3.2.3 Vital Signs**

Vital signs will be collected during all study assessment timepoints from Baseline to 40 Weeks PMA/Hospital Discharge. On Day 1, vital signs are to be collected 7 times: just prior to dosing, at the midpoint of dosing, just after the end of dosing, and at least once every hour for the first 4 hours after the completion of dosing.

Vital signs measured will include systemic blood pressure (systolic and diastolic), heart rate, and respiratory rate (either spontaneous rate or the sum of spontaneous rate and mechanically delivered rate). Except for dose administration, no other measurements or procedures should be performed during measurement of vital signs. Vital signs should also be assessed in the case of abnormal clinical signs and symptoms.

**3.3.2.4 Adverse Events**

All AEs will be documented from the time of informed consent until the time screen failure is documented, or until the subject is either discontinued from the study or all 40 Weeks PMA/Hospital Discharge assessments have been completed and should be followed until either resolution (or return to normal or baseline values), until they are judged by the Investigator to no longer be clinically significant, or for at least 30 days if the AE extends beyond the Post-treatment Phase.

All AEs meeting the criteria for serious (ie, serious adverse events [SAEs]) should be followed until resolution, death, or the subject is lost to follow-up even if they are ongoing more than 30 days after completion of the Post-treatment Phase

Refer to Section 9.1 for detailed definitions of safety events. All AEs/SAEs that occur during the study will be followed as instructed in Section 9.3.

If, at any time, the parent/guardian withdraws their consent for the subject to remain in the study, any AEs/SAEs that occur from UNEX-42 treatment (including product use errors, product quality problems, and therapeutic failures) will be reported. These events will not be recorded in the electronic Case Report Form (eCRF).

### **3.3.2.5 Predefined Complications of Prematurity**

Complications of prematurity will be assessed from Baseline to 40 Weeks PMA/Hospital Discharge. The diagnosis of the following complications will be recorded: sepsis, pneumothorax, clinically significant patent ductus arteriosus (PDA) requiring treatment or ligation, necrotizing enterocolitis requiring treatment or surgery, intraventricular hemorrhage (including highest grade), periventricular leukomalacia, and retinopathy of prematurity (including stage).

### **3.3.2.6 Clinical Laboratory Parameters**

Blood samples for the clinical chemistry and hematology analyses will be collected at Baseline (randomization) and repeated at the 72 hours postdose and the 36 Weeks PMA assessments to evaluate for study treatment-emergent changes. For Baseline, the clinical laboratory assessments may utilize the laboratory assessments obtained as standard of care treatment within the last 24 hours in lieu of drawing blood for the sole purpose of the study. Any study-required blood tests should be obtained at the same time a blood sample is being collected for clinical purposes, if possible. Values for the following parameters will be obtained:

**Table 3-5 Clinical Laboratory Parameters**

Electrolyte Panel	Chemistry Panel	Hematology Panel
Bicarbonate	Alanine aminotransferase	Hemoglobin
Chloride	Aspartate aminotransferase	Hematocrit
Potassium	Bilirubin (total and indirect)	Red blood cell count
Sodium	Creatinine	White blood cell count
	Blood urea nitrogen	Platelet count

**3.4 NUMBER OF CENTERS**

This is a US-based multicenter study with approximately 6 centers participating.

**3.5 NUMBER OF SUBJECTS**

Approximately 18 subjects will be enrolled in this study. There will be 3 cohorts of 6 subjects per cohort, randomized 2:1 (active:placebo) for a total of 12 subjects receiving UNEX-42 treatment (4 subjects each at 20, 60, and 200 pmol phospholipid/kg body weight) and 6 subjects receiving placebo.

**3.6 ESTIMATED STUDY DURATION**

The expected duration for a subject to complete the study is up to 69 weeks. Subjects are administered clinical study material (CSM) on Day 1 and the Post-treatment Phase will consist of assessments through 40 Weeks PMA (up to 17 weeks depending on subject GA at birth). Subjects that complete the Post-treatment Phase (including those that are discharged from hospital prior to 40 Weeks PMA) will continue into the Long-term Outcome Phase and will be assessed through 1 year of corrected age. Analysis of data from the Post-treatment Phase will occur after all subjects have completed the Post-treatment Phase.

**4 SUBJECT ELIGIBILITY**

Inclusion and exclusion criteria are to be assessed at Screening and reconfirmed at Baseline prior to randomization.

#### 4.1 INCLUSION CRITERIA

A subject must meet the following criteria to be eligible for the study:

1. Infant whose postnatal age is 3 to 14 days at randomization.
2. Subject meets the following oxygen and birth weight criteria based on GA:

Gestational Age at Birth	Criteria
23 weeks to 24 weeks 6 days	Any birth weight, any oxygen requirement
25 weeks to 26 weeks 6 days	$\text{FiO}_2 \geq 35\%$ (sustained >2 hours) at any point during postnatal Days 1 to 14 AND birth weight $\leq 750$ g

3. Endotracheally intubated and receiving mechanical ventilation at the time of Screening and randomization.
4. Not expected to be extubated within the next 24 hours after randomization.
5. The subject has a parent/guardian who gives written informed consent.

#### 4.2 EXCLUSION CRITERIA

A subject is not eligible for inclusion in this study if any of the following criteria apply:

1. Has a congenital heart defect, except for PDA, atrial septal defect or a small/moderate, restrictive ventricular septal defect.
2. Has a serious malformation of the lung, such as pulmonary hypoplasia/aplasia, congenital diaphragmatic hernia, or any other congenital lung anomaly.
3. Being treated with inhaled nitric oxide.
4. Has a known chromosomal abnormality (eg, Trisomy 18, Trisomy 13, or Trisomy 21) or a severe congenital malformation (eg, hydrocephalus and encephalocele, trachea-esophageal fistula, abdominal wall defects, and major renal anomalies).
5. Has had a known severe congenital infectious disease (ie, herpes, toxoplasmosis rubella, syphilis, human immunodeficiency virus, cytomegalovirus, etc).
6. High clinical suspicion of active systemic infection, severe sepsis, or septic shock during the Screening period.
7. Underwent a surgical procedure (requiring admission to an operating room) within 72 hours before randomization or who is anticipated to have a surgical procedure (requiring admission to an operating room) within 72 hours before or following randomization.
8. Has had a Grade 3 or 4 intracranial hemorrhage.
9. Has active pulmonary hemorrhage.
10. The subject is currently participating in any other interventional clinical study.
11. The subject is, in the opinion of the Investigator, so ill that death is inevitable, or is considered inappropriate for the study for any reason(s) other than those listed above.

## 4.3 PRESCRIBED THERAPY

Not applicable.

### 4.3.1 Concomitant Medications

All concomitant medications taken during the Post-treatment Phase of the study, including those that are ongoing at Baseline or taken for AEs or other medical events, should be recorded in the subject's source documents and transcribed as required to the eCRF.

## 5 SUBJECT ENROLLMENT

### 5.1 TREATMENT ASSIGNMENT

Within each cohort, eligible subjects will be randomly allocated to receive either UNEX-42 or placebo at randomization (using a 2:1 allocation ratio). A subject number will be assigned to identify individual subject data. An Interactive Response Technology (IRT) will be responsible for allocation of all study drug.

### 5.2 RANDOMIZATION

The study will be randomized 2:1 UNEX-42 to placebo. Within each dose cohort, subjects will be randomly allocated to receive UNEX-42 or placebo through the IRT using a centrally administered block randomization.

### 5.3 BLINDING

The Investigator, study site personnel involved in preparation/administration of CSM, subject's parent/guardian, and Sponsor (except for Global Drug Safety and Regulatory Affairs personnel involved in safety reporting) will not be aware of the treatment allocation. All CSM will be provided as blinded study drug.

## 6 TREATMENT PROCEDURES

### 6.1 UNEX-42 DOSAGE AND ADMINISTRATION

UNEX-42 will be administered to 3 cohorts at 20, 60, and 200 pmol phospholipid/kg body weight, respectively, in a dose-escalating manner. UNEX-42 is suspended in phosphate-buffered saline. UNEX-42 is a clear liquid that is provided in appropriately sized vials and stored at  $-70\pm10^{\circ}\text{C}$  prior to use. UNEX-42 will be appropriately diluted in normal saline to achieve a final dosing volume of 1 mL.

Once all entry criteria have been met and random treatment assignment confirmed, the dose of CSM will be prepared by the site pharmacy staff. The filled syringe of CSM will be delivered to the hospital room and administered to the subject by appropriately trained staff. The CSM must be administered within 8 hours after thawing. The CSM should be administered through an existing IV catheter being used for administration of crystalloids, such as an umbilical, central, or peripheral IV line. If any circumstances prevent administration of CSM through an existing IV line, a new IV line may be started for the administration of CSM at the discretion of the Investigator. If necessary, the line for infusion must first be flushed and primed with a sufficient volume of normal saline to clear the line at a controlled rate of 10 mL/hour by a syringe pump, regardless of subject weight. The CSM syringe contents will then be administered at a controlled rate of 10 mL/hour by a syringe pump. Once the CSM has been completely administered, the line will be flushed with a sufficient volume of normal saline to clear the CSM from the line at a controlled rate of 10 mL/hour.

CSM infusions may be stopped at the discretion of the Investigator if any of the following are observed during the course of the infusion or the flush:

- Acute worsening of respiratory function requiring intervention.
- Acute hypotension requiring intervention (including but not limited to fluid bolus, vasopressors, or hydrocortisone).
- Any acute change in vital signs requiring medical intervention.
- Any other medical issue such that, in the opinion of the Investigator, continuation of study drug infusion represents a serious medical risk to the subject.

Subjects that receive any amount of CSM will be followed for the duration of the study, unless the subject is withdrawn from the study as described in Section 8.1 of the protocol.

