## PROTOCOL SYNOPSIS

Title	A Safety Study of Intravenous Infusion of Bone Marrow Mesenchymal Stem Cell-derived Extracellular Vesicles (UNEX-42) in Preterm Neonates at High Risk for Bronchopulmonary Dysplasia
Study Phase	Phase 1
Indication	Bronchopulmonary dysplasia (BPD) prevention in preterm infants
Primary Objective	To assess the safety and tolerability of intravenous (IV) infusion of UNEX-42 in infants born at <27 weeks of gestational age (GA) and exhibiting respiratory distress.
Secondary Objective(s)	
To assess the effect of UNEX-42 on the following:
 
 
Incidence and severity (mild, moderate, severe) of BPD or death at 36 weeks postmenstrual age (PMA)
 
Short-term outcomes including oxygen and ventilation exposure in the first 28 days after treatment.
 
Long-term outcomes up to 1 year (corrected age).
 

Study Design	A multicenter, placebo-controlled, randomized, dose escalation, safety, and tolerability study of UNEX-42 in infants born at <27 weeks of GA at high risk for BPD
Sample Size	Target enrollment of 18 total subjects, with 3 cohorts of 6 subjects per cohort, randomly allocated 2:1 (active:placebo)
Summary of Subject Eligibility Criteria	
A subject must meet the following criteria to be eligible for the study:
 
 
Infant whose postnatal age is 3 to 14 days at randomization and meets the following criteria based on GA: 
 
23 weeks to 24 weeks 6 days: any birth weight, any oxygen requirement
 
25 weeks to 26 weeks 6 days: fraction of inspired oxygen (FiO2) ≥35% (sustained >2 hours) at any point during postnatal Days 1 to 14 AND birth weight ≤750 g
 
 
 
Endotracheally intubated and receiving mechanical ventilation
 
Not expected to be extubated within the next 24 hours after randomization
 
The subject has a parent/guardian who gives written informed consent.
 

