Drug Dosage and Formulation	
UNEX-42 is a preparation of extracellular vesicles that are secreted from human bone marrow-derived mesenchymal stem cells suspended in phosphate-buffered saline. UNEX-42 is a clear liquid that is provided in appropriately sized vials and stored at -70±10°C prior to use.
 
UNEX-42 will be administered via IV infusion. Three dose cohorts will be evaluated:
 
 
Cohort 1: 1 administration of 20 pmol phospholipid/kg body weight
 
Cohort 2: 1 administration of 60 pmol phospholipid/kg body weight
 
Cohort 3: 1 administration of 200 pmol phospholipid/kg body weight
 

Control Group	Placebo (phosphate-buffered saline)
Route of Administration	IV infusion (via umbilical/central/peripheral IV line)

Procedures	
Subjects will be assessed during Screening and Baseline (prior to randomization) to determine eligibility for the study. After randomization, subjects will be monitored in the hospital through 40 Weeks PMA or the time of hospital discharge (whichever comes first).
 
The following efficacy and safety assessments will occur during the course of the study:
 
Efficacy Assessments: incidence and severity of BPD, duration of hospitalization, duration of mechanical ventilation, duration of supplemental oxygen therapy, duration of postnatal steroids, tracheal aspirate, and Respiratory Severity Score.
 
Safety Assessments: physical examination, vital signs, adverse events, predefined complications of prematurity, clinical laboratory parameters, and chest x-ray.
 
Enrollment between cohorts will pause for data review by a Data Monitoring Committee to evaluate the data available after each of the first 2 cohorts have been enrolled. Dose administration for Cohort 1 will occur such that there is an observational period of 3 days between dosing the first, second, and third subject to assure the opportunity for safety assessments in at least 1 subject on active treatment. This procedure will be followed for each cohort.
 
Subjects that complete the Post-treatment Phase (including those that are discharged from hospital prior to 40 Weeks PMA) will continue into the Long-term Outcome Phase and will be assessed through 1 year of corrected age.

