# **11 PACKAGING AND FORMULATION**

## **11.1 CONTENTS OF STUDY DRUG**

United Therapeutics will supply UNEX-42 for administration in the study. UNEX-42 will be provided in 5-mL vials each containing 2 mL of sterile solution. The phospholipid content of the solution will be expected to be 100 to 500 pmol/mL. The exact concentration will be provided at the time of CSM manufacture and release testing.

Placebo will be phosphate-buffered saline provided in vials matching UNEX-42 in color, size, and shape.

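### In Cohort 3 the fixed 1 mL dosing volume cannot hold the full dose for a 750 g infant if the product is below 150 pmol/mL, although strengths down to 100 pmol/mL are expected

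*Protocol*

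**What the plan says.** Section 6.1 of the protocol covers all three dose levels with a single preparation instruction: "UNEX-42 will be appropriately diluted in normal saline to achieve a final dosing volume of 1 mL". The same section fixes the infusion rate: "The CSM syringe contents will then be administered at a controlled rate of 10 mL/hour by a syringe pump".

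The top dose is in the Synopsis: "Cohort 3: 1 administration of 200 pmol phospholipid/kg body weight".

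Product strength and vial fill are in Section 11.1: "The phospholipid content of the solution will be expected to be 100 to 500 pmol/mL" and "UNEX-42 will be provided in 5-mL vials each containing 2 mL of sterile solution". That section adds that the actual strength is reported at manufacture and release.

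Eligible weight depends on gestational age. For 25 weeks to 26 weeks 6 days, the Synopsis requires an oxygen criterion within "postnatal Days 1 to 14 AND birth weight ≤750 g". For 23 weeks to 24 weeks 6 days, Section 4.1 accepts "Any birth weight, any oxygen requirement". A 750 g infant can therefore enter from either stratum, and the younger stratum has no upper weight limit.

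Neither document sets a minimum strength for Cohort 3, a step to concentrate the product, an exception to 1 mL, or a ceiling on the absolute dose.

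**The concern.** Dilution can only lower a concentration. The full dose therefore fits in 1 mL only if the undiluted product that carries it occupies 1 mL or less. Dose per kg, weight and strength all vary while the final volume does not, so the instruction has to be checked at the highest dose and the lowest expected strength. It fails there.

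What is at stake is the actual dose in the top cohort. Section 3.5 puts only 4 infants on active drug at 200 pmol/kg, so one infant dosed well below target is a quarter of the safety experience at that level. Section 6.5 makes the site responsible for giving the right dose, but with such a lot the site could not meet both the dose and the volume instruction, and the protocol has no rule for that case.

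**Working it through.** **Inputs**

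- Dose D: 20, 60 and 200 pmol/kg (Synopsis; Section 6.1)
- Final volume: 1 mL (Section 6.1)
- Strength C: 100 to 500 pmol/mL (Section 11.1)
- Vial fill: 2 mL (Section 11.1)
- Weight W: 0.75 kg, the birth-weight limit of the older stratum (Synopsis; Section 4.1). A weight of 1.0 kg is also used, as an assumption, because the younger stratum has no limit.

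**The plan's own figure.** The protocol gives no derivation of the 1 mL, so it cannot be reproduced. It can only be tested for feasibility.

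**Volume needed.** Undiluted volume = D x W / C. This must not exceed 1 mL, so the minimum strength is D x W per mL. For Cohort 3 at 750 g:

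- Amount: 200 x 0.75 = 150 pmol
- Minimum strength for 1 mL: 150 pmol/mL
- At 100 pmol/mL: 150 / 100 = 1.50 mL, which does not fit
- At 500 pmol/mL: 150 / 500 = 0.30 mL, which fits

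**Dose delivered if the volume is held at 1 mL.** Delivered dose = C / 0.75, and shortfall = 1 - delivered / 200.

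| Strength (pmol/mL) | Volume needed (mL) | Delivered in 1 mL (pmol/kg) | Shortfall |
|---|---|---|---|
| 100 | 1.50 | 133 | 33% |
| 110 | 1.36 | 147 | 27% |
| 120 | 1.25 | 160 | 20% |
| 130 | 1.15 | 173 | 13% |
| 140 | 1.07 | 187 | 7% |
| 150 | 1.00 | 200 | 0% |

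**Largest weight that fits in 1 mL.** Weight = C / D.

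- At 100 pmol/mL: Cohort 1, 100 / 20 = 5.0 kg; Cohort 2, 100 / 60 = 1.67 kg; Cohort 3, 100 / 200 = 0.50 kg
- Cohort 3 at 150, 200 and 500 pmol/mL: 0.75, 1.0 and 2.5 kg

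Only Cohort 3 is affected at these weights. At 750 g and 100 pmol/mL, Cohorts 1 and 2 need 15 / 100 = 0.15 mL and 45 / 100 = 0.45 mL.

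**Sensitivity to weight.** The Cohort 3 threshold is 200 x W, or 0.2 pmol/mL per gram: 100 pmol/mL at 500 g, 120 at 600 g, 150 at 750 g and 200 at 1.0 kg.

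**Vial content is not the limit.** One vial at 100 pmol/mL holds 2 x 100 = 200 pmol, more than the 150 pmol needed at 750 g. A second vial does not help, because the final volume is what binds.

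**The case against.** The best case for the plan is that the problem needs a lot that may never reach Cohort 3. Section 11.1 states an expected range, not a promise to ship product at its lower end. The sponsor knows each lot's strength at release, resupplies sites (Section 11.4), and has enrollment pauses before Cohort 3 (Sections 10.4 and 10.7) in which it could set stronger lots aside. A lot-selection rule may also exist in product documents outside these two. The chosen weight is near the edge: at 500 g or less there is no conflict anywhere in the range. Even the 750 g worst case gives 133 pmol/kg, more than twice the Cohort 2 dose (133 / 60 = 2.2), so the order of the doses is kept. All of this stands, and it limits the consequence. It does not remove the conflict, because nothing in the protocol requires stronger lots for Cohort 3.

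A reader might infer three stronger claims that the documents do not support.

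- **That staff must either underdose or break the 1 mL rule.** They could also query the sponsor and obtain a stronger lot. Strength is known and the amount given is recorded (Sections 6.5, 11.1 and 11.5), so unnoticed underdosing is not the expected result.
- **That blinding is threatened,** because 1.5 mL at 10 mL/hour runs 9 minutes and 1 mL runs 6. Section 5.3 keeps "The Investigator, study site personnel involved in preparation/administration of CSM" unaware of allocation, so they could not knowingly enlarge the volume for active drug alone. How strength is presented for placebo vials is not stated.
- **That the risk is about one in eight,** because (150 - 100) / (500 - 100) = 12.5% of the range fails at 750 g. That is a share of the range's width. The documents give no distribution of lot strengths.

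**Conclusion.** Wrong as written, and minor. The 1 mL volume in Section 6.1 is not compatible with the full strength range in Section 11.1 for Cohort 3. For a 750 g infant it holds from 150 to 500 pmol/mL and fails below that, by up to 33% of the dose at 100 pmol/mL.

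The arithmetic is certain given the protocol's inputs. The practical consequence is not: it depends on a low-strength lot being allocated to Cohort 3. The result also takes 750 g as the dosing weight, whereas 750 g is a birth-weight limit and dosing follows 3 to 14 days after birth. A different dosing weight moves the threshold in proportion.

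No infant was affected. SAP Section 1.1 records that the study ended with 3 subjects randomized in the first cohort. The point concerns the protocol text and any reuse of it.

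**What to change.** In Sections 6.1 and 11.1, state two things:

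1. A Cohort 3 infant may be dosed only from a lot whose strength in pmol/mL is at least 200 times that infant's dosing weight in kg.
2. Cohort 3 is supplied only with lots of at least 200 pmol/mL.

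The supply floor covers infants up to 1 kg; a floor of 150 pmol/mL would cover only 750 g. The per-infant rule is still needed because infants of 23 to 24 weeks have no weight limit, so no single floor below the top of the range is guaranteed to cover everyone. The check should be made for every Cohort 3 infant regardless of allocation, against the active lot held for the cohort. The 1 mL volume and 6-minute infusion then stay the same in both arms.

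The cost is a sentence or two of protocol text and the possible loss of some lots for Cohort 3. The floor excludes strengths from 100 to just under 200 pmol/mL, which is 100 / 400 = 25% of the width of the stated range; the share of lots is unknown. Those strengths would still fit Cohorts 1 and 2. Doses, sample size and escalation steps do not change.
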